## **List of Specific Aims**

1. To refine the program, "Improving Care through Improv" for informal dementia care partners.
2. To assess the feasibility, acceptability, and preliminary efficacy of "Improving Care through Improv" through pilot testing

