## **Brief Description of Project Design**

- Phase 1 involves refining the training program, "Improving Care through Improv" (Aim 1).
- Phase 2 involves piloting the training program with 40 adult informal care partners of person with moderate dementia to test its effect on self-perceived caregiving mastery through a no-control, pre-post design single-group trial with three time points: baseline; immediately upon completion, and 3-months post baseline (Aim2). The intervention will be delivered to up to 5 groups of 8 to 12 participants each. All groups will be exposed to the same in-person training during weekly 2-hour sessions held over a 4-week period. At 3-months post baseline, there will be a 90-minute in-person session to allow for completion of the assessment and to obtain participant feedback.

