## **Procedures/Human Subjects Involvement**

Study participants will be exposed to the same in-person group training delivered by study personnel during weekly 2-hour sessions held over a 4-week period. In addition to the four in-person training sessions, participants will be invited to attend a final one-and-a-half hour in-person group meeting, which will involve completion of the 3-month post baseline assessment and invite feedback on the overall intervention experience through

open-ended questions. Participants will complete a self-administered pen and paper survey at all three study time points: baseline; upon training completion; and 3-months post baseline. At baseline, we will collect care partners' demographic details (e.g., age, gender, race, ethnicity, employment status, education, urban/suburban/rural status, relationship to care recipient), and key information pertaining to their caregiving history, experiences, and care recipient.

At all three time points, participants will be asked to complete measures to assess: caregiver mastery, self-perceived stress, anxiety, caregiver burden, and perceived changes in care recipients' behavioral expressions and with associated care partner distress. We also will ask participants to assess their care recipients' quality of life. Participants will complete these self-administered surveys in person with researchers present to answer any questions. The surveys collected at baseline and upon training completion will be distributed and completed at the first and fourth training sessions, respectively.

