### **Inclusion Criteria**

Eligible participants will be: 1) 18-years or older; 2) actively engaged in the care of community-dwelling persons living with moderate dementia (4 or 5 on a 7-point dementia-staging scale) who is not likely to be institutionalized within the next 6 months; 3) able to attend at least 3 of the 4 in-person sessions. Participants also will need to be able to read, write, and communicate in English. Screening will take place over the phone when potential participants reach out to the study team and express interest in the study.

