### **Benefits & Risks**

Study participants may benefit by having opportunities throughout the training to share their experiences and perspectives with others. In past, we have found that research participants enjoy the opportunity to talk about their experiences. The group-based interactions also will provide a social outlet, which they may find enjoyable. We anticipate that the training they receive will give them new skills and techniques to use as they perform their care roles. Ideally, these skills, including an ability to "be in the moment," may enhance their self-perceived caregiver mastery and possibly their self-

reported burden, anxiety, depression, perceptions of care recipients' behavioral expressions and associated care-partner distress and quality of life. We will not state to participants that taking part in the training program will be beneficial to them, although we believe and are hopeful that it will. We also will acknowledge that study participation may eventually contribute to the well-being of other informal care partners. If this intervention shows signs of efficacy, we will pursue additional funding to conduct further tests and ideally scale up the intervention in size and scope, including for instance, training for formal care partners and others. Improv training has the potential to improve dementia care experiences for all types of care partners, health care workers, and others who engage with persons living with dementia in all types of settings.

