### **Data Analysis Plan**

Descriptive statistics will be calculated for all demographics and instrument scores at baseline, completion, and three months after baseline. Internal reliability will be assessed using Cronbach's alpha at baseline. Missingness will be assessed and corrective measures used as appropriate (multiple imputation). Repeated measures analysis of variance will be used with dependent variables across the three time points. Error rate adjustments (Bonferroni or Dunn-Sidak tests) will be made due to the implementation of multiple comparisons across dependent variables. Effect sizes will also be computed and assessed for clinical significance. The percentages of caregivers whose scores improve or decline from baseline to completion and post-completion assessments will be calculated. IBM SPSS for Windows, version 24.0 will be used to perform computations.

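### Do the improved/declined percentages need a written cut-off, denominator and confidence interval?

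*Combined protocol and SAP*

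**What the plan says.** The sentence at issue is in the Data Analysis Plan: "The percentages of caregivers whose scores improve or decline from baseline to completion and post-completion assessments will be calculated". It gives no minimum change, no category for unchanged scores, no denominator and no interval.

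Four other parts of the document bear on it:

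- **Survey timing.** Procedures/Human Subjects Involvement says the baseline and completion surveys are "distributed and completed at the first and fourth training sessions, respectively". The three-month survey is filled in at a further meeting to which participants are invited. No make-up survey is described.
- **Attendance.** Inclusion Criteria asks that a person be "able to attend at least 3 of the 4 in-person sessions".
- **Outcomes.** Procedures lists "caregiver mastery, self-perceived stress, anxiety, caregiver burden", then care recipients' behavioural expressions with the related care-partner distress, then care recipients' quality of life.
- **Inference.** The Data Analysis Plan analyses the outcomes over the three time points by repeated-measures analysis of variance, with a Bonferroni or Dunn-Sidak correction across outcomes. It adds effect sizes judged for clinical significance, and multiple imputation where appropriate.

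**The concern.** Two analysts could follow the sentence faithfully and print different percentages. One might count any change and another might require a minimum change. One might divide by those with both scores, another by everyone enrolled, and a third might use imputed scores. The design makes this more than a quibble, since a person can meet the attendance criterion and still miss session 1 or session 4, and so have no baseline-to-completion pair.

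The figures could also be over-read. The second aim is "To assess the feasibility, acceptability, and preliminary efficacy of" the programme, and Benefits & Risks adds "If this intervention shows signs of efficacy, we will pursue additional funding to conduct further tests" without defining such a sign. The design is a "no-control, pre-post design single-group trial with three time points", so a large improved share has nothing to be compared with. Across many outcomes and two intervals, some will show more improvers than decliners by chance. If funding or scale-up rested on such a figure, the missing definitions and intervals would matter.

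**Working it through.** The plan gives no figure to reproduce. It states no SDs, correlations, attendance rates or named instruments, so every input below other than the counts of people, outcomes and sessions is an assumption.

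**1. Number of summaries.** Mastery, stress, anxiety, burden, behavioural expressions and quality of life make 6 scores, or 7 if distress is scored separately. With two intervals: 6 × 2 = 12, or 7 × 2 = 14.

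**2. How many lack a pair.** If a fraction f of participants miss one of the four sessions at random, half of those absences fall on session 1 or 4. With f = 20-40%, f/2 = 10-20%, which is 4-8 of 40. If only sessions 2-4 are ever missed, f/3 = 7-13%.

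**3. Effect of the denominator.** Simulated improved share (%), n = 40, retest correlation 0.7, whole-point scores, absences unrelated to outcome, imputed values left unrounded:

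| True gain | Unpaired | SD | Both scores | Imputed | All enrolled |
|---|---|---|---|---|---|
| none | 10% | 1.5 | 33.8 | 35.5 | 30.5 |
| none | 10% | 8 | 47.1 | 47.3 | 42.3 |
| none | 20% | 1.5 | 33.7 | 37.0 | 26.9 |
| none | 20% | 8 | 46.9 | 47.5 | 37.5 |
| 0.5 SD | 20% | 1.5 | 58.3 | 61.1 | 46.6 |
| 0.5 SD | 20% | 3 | 66.6 | 67.9 | 53.3 |
| 0.5 SD | 20% | 8 | 71.7 | 71.9 | 57.3 |

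Observed pairs and imputation differ by 0.2 points (47.3 − 47.1) to 3.3 points (37.0 − 33.7). Observed pairs and all enrolled differ by 3.3 points (33.8 − 30.5) to 14.4 points (71.7 − 57.3). That second difference is simply the unpaired fraction times the improved share, for example 0.20 × 66.6 = 13.3. It arises only if people without a pair are counted as not improved.

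**4. Effect of the cut-off.** With retest correlation r, the change score has SD √(2(1 − r)) in baseline SD units; at r = 0.7 this is 0.775. For a true mean gain of 0.3 SD and cut-off c, improved = 1 − Φ((c − 0.3)/0.775) and declined = Φ((−c − 0.3)/0.775):

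| Cut-off | Improved | Declined | Difference |
|---|---|---|---|
| any change | 65.1% | 34.9% | 30.2 |
| 0.2 SD | 55.1% | 25.9% | 29.2 |
| 0.5 SD | 39.8% | 15.1% | 24.7 |

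The cut-off moves the improved share by up to 25 points, but the balance of improvers over decliners moves much less and keeps its direction.

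**5. Chance differences.** With no true change and n = 40 (SD 1-15, retest correlation 0.6-0.8, between-scale correlation 0-0.7), one summary favours the programme by 20 points or more 4-13% of the time, and at least one of 12-14 does so 28-79% of the time.

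**6. What an interval would add.** For a improved and d declined of n, let p = (a+1)/(n+2) and q = (d+1)/(n+2). The interval is p − q ± z√((p + q − (p − q)²)/(n + 2)). With 20 improved, 12 declined and 8 unchanged of 40: p = 21/42 = 0.500, q = 13/42 = 0.310, standard error √((0.810 − 0.036)/42) = 0.136. The 95% interval is 19.0 ± 26.6, that is −7.5 to 45.6 points. A reader can compute this from the two percentages and n.

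**7. What adjusted intervals would cost.** For one scale, n = 40, SD 1.5-8 and retest correlation 0.6-0.8, the share of trials whose lower limit is above zero is:

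| True gain | Unadjusted 95% | Bonferroni, 12-14 summaries |
|---|---|---|
| 0.5 SD | 83-99% | about 49-91% |
| 0.3 SD | 42-72% | about 13-39% |

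**The case for a change.** The best case for acting is that the omissions are real and cheap to repair. No other section supplies a definition, the survey timing does let an eligible person go unpaired, and the imputation sentence is not tied to these percentages. A claim that two thirds of caregivers improved is easy to quote from an uncontrolled pilot, yet with no true change 24-49% would show some improvement at SD 1-15. A few sentences would fix the rule in advance.

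The factual part stands. Step 4 also shows that an unannounced cut-off could change the headline share materially, so a published percentage must say what it counts.

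The consequence does not stand. The improved-minus-declined difference is not something the plan proposes or draws inference from, and the planned analysis of variance already tests the same scores with a multiplicity correction. The funding remark in Benefits & Risks leads only to further testing and is not linked to these percentages. Nor would an interval replace a control group, since it leaves time trend, regression to the mean and response bias untouched. The assumed 20-40% absence rate has no basis in the document. The criterion is a floor for eligibility, Participants and Recruitment has staff schedule around participants' availability, and Participant Compensation pays $75 per session.

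**Conclusion.** No change to the plan is needed. This is an unwritten definition for one descriptive sentence in a 40-person single-group pilot, and analysts would fill it sensibly: any change in the stated direction, among caregivers with both scores, with the number of pairs shown as in any ordinary table. Following the plan that way gives no wrong result. Against multiple imputation, the only alternative the text mentions, the improved share moves by 0.2-3.3 points. That range assumes 10-20% unpaired, retest correlation 0.7, SD 1.5-8 and absences unrelated to outcome. If those who miss a survey differ systematically, both readings could be biased, and a written denominator would not cure that.

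The adjusted analysis of variance and effect sizes carry the inference. An unadjusted interval is easily derived from the reported counts. A Bonferroni interval across 12-14 summaries is at best a debatable trade, since at a 0.3 SD gain it would exclude zero in only about 13-39% of trials.

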### **Informed Consent**

See Appendix A

